8 RESEARCH QUESTION AND OBJECTIVES

The research questions for this study is: Were the key safety messages in the healthcare professional guide and the patient guide, implemented as risk minimisation measures (RMM) beyond routine, effective in:

- Providing a good knowledge and understanding to health care professionals (HCPs) who prescribed or dispensed SULIQUA and to patients treated with SULIQUA
- Reducing the risk of medication errors when prescribing/delivering or using SULIQUA

The main objective of this study is to assess the knowledge and understanding of the key safety messages in the healthcare professional guide and patient guide among HCPs who prescribed or dispensed SULIQUA and patients treated with SULIQUA, respectively.

Specific objectives are to assess the proportion of:

- HCPs:
 - Who receive, understand and implement the safety messages conveyed by EM for SULIQUA
 - Who are aware that prescriptions for SULIQUA should state clearly the dose range and strength of SULIQUA in a pre-filled pen and the number of dose steps to be administered by the patient
 - Who advise patients with regard to dose steps required, design, features and appropriate utilization of SULIQUA pre-filled pen, close monitoring of blood sugar levels after initiation, and anticipated adverse reactions
 - Who noted medication errors in treated patients
- Patients/caregivers
 - Who acknowledge receiving SULIQUA pre-filled pen guide for patients and caregivers
 - Who read the patient guide before using SULIQUA pre-filled pen
 - Who implemented the safe utilisation of SULIQUA according to safety information for the SULIQUA pre-filled pen
 - Who were trained/advised by their HCP (physician or pharmacist) on how to use SULIQUA pre-filled pen

9 RESEARCH METHODS

9.1 STUDY DESIGN

This survey will be cross-sectional, multinational, multichannel and conducted among HCPs as well as patients/caregivers in 3 waves.

There will be two questionnaires, one designed for the HCPs and another designed for patients/caregivers. These questionnaires include the following sections:

Table 1: Sections of HCP's and patient's questionnaires

HCP Questionnaire	Patient/Caregiver Questionnaire
Screening section (items S1-S3)	Screening section (items S1-S2)
HCP practice information (items D1-D3)	Questionnaire (items S3-S6, Q1-Q7)
Prescribing/delivery conditions and safety information (items Q1-Q10)	

The survey will be conducted primarily through a web questionnaire. Paper questionnaires will be additionally proposed to patients and phone questionnaires to HCPs who would not be able to answer the survey online.

In each country, HCPs will be identified according to their specialty (general practitioners [GP], endocrinologist/diabetologist, internists, gastroenterologists, pharmacists, nurse, geriatrists) as specified in OneKey lists (IQVIA). OneKey is the most comprehensive worldwide database of HCPs. It is constructed according to ISO 9001: 2015 Quality Management Systems Requirements. The lists are representative of the HCPs population in the selected countries.

For patients recruitment, HCPs to be contacted will be randomly selected according to the procedure described in the sampling plan section (Section 9.2.4). They will be sent patient kits for distribution to the patients.

9.2 SETTING

The survey will be conducted in selected European countries in 3 waves. Each wave will correspond to the sequential inclusion of the targeted countries according to the timing of SULIQUA launch and implementation of RMM in these countries. Furthermore, the selection of countries to be involved in each wave of the survey will take into account the following criteria:

- Where SULIQUA has been registered and both pens were marketed for at least 6 months at the start of the survey (Table 2)
- Where the HCPs have been targeted for the EM and direct healthcare professional communication (DHPC) at the start of the survey
- where SULIQUA availability and market penetration is sufficiently high to allow HCPs participation

The MAH will therefore take into account the predicted market uptake to preselect the countries and will ensure that the study will be performed in countries where SULIQUA (both pens) is available and accessible to patients. The exact list of participating countries is currently being refined.

Table 2, below, shows the provisional timetable for commercial launch of SULIQUA in selected European countries. Dates are projections and may be subject to change during the course of the study. The list of countries participating in each wave will be finalized before each wave starts according to the effective launch date.

Table 2: List of candidate countries to be included in the successive waves according to SULIQUA provisional dates when both pens were made available to patients in EU (source Sanofi-Aventis Group)

Country	Available to patients (both pens)	Wave		
		1	2	3*
Hungary	09 October 2017	X	-	
Czech Republic	02 May 2018	X	-	
Slovenia	01 June 2018	X	-	To be determined
Romania	05 June 2018 (peach pen) 23 April 2019 (olive pen)	-	X	
Croatia	Q3 2019	-	X	
Belgium	01 November 2018	-	X	
United Kingdom	10 May 2019 (olive) 17 May 2019 (peach)	-	X	

X refers to candidate to be included in the present wave

*The details on countries will be updated if Wave 3 is deemed feasible at the time of Wave 2 report submission.

Essentially, countries selected will be different from one wave to the next wave based on the actual market penetration and product availability to patients. Croatia is at risk and Italy has been dropped from this study due to challenges related to the ethics committee (EC) approvals. Latvia was planned as a candidate country for Wave 1 but was dropped from the survey due to difficulties to setup the study. Wave 3 countries are yet to be determined, and for this the MAH will continue monitoring which additional countries can be added and provide an update on the sales data (i.e. product launch and market uptake) in the interim reports.

The first wave of survey includes the countries in which EM were distributed from the end of Q4 2017. A total of 150 HCPs and 150 patients/caregivers will be included in Wave 1.

The second wave of the survey will include countries in which EM were distributed from Q3 2018. A total of 150 HCPs and 150 patients/caregivers will be included in Wave 2. If the sample size is difficult to reach, the countries in which EM were distributed in a following quarter, i.e. Q3-Q4 2019 but which were not included in Wave 1, will be included in Wave 2.

The third wave of the survey will include countries in which EM will be distributed from Q3 2019. A total of 150 HCPs and 150 patients/caregivers will be included in Wave 3. If the sample size is difficult to reach, the countries in which EM were distributed earlier will be included in Wave 3.

9.2.1 Duration of the study

The Wave 1 of the survey started in September 2019. The interim study report of Wave 1 will be submitted to EMA in November 2020. The final report of results of this study is planned to be submitted in June 2022 to EMA.

9.2.2 Eligibility criteria

9.2.2.1 Inclusion criteria

The HCP survey will be conducted among HCPs meeting the following inclusion criteria:

- HCPs who prescribe/deliver SULIQUA

The patient survey will be conducted among patients (or their caregivers) meeting the following inclusion criteria:

- Respondents (patients or caregivers of a patient) who receive SULIQUA

9.2.2.2 Exclusion criteria

HCP survey

The following exclusion criteria will be checked at the beginning of the web questionnaire:

- HCPs who are not involved in patient treatment
- HCPs who may have conflicts of interest with the survey (i.e. HCPs employed by regulatory bodies, pharmaceutical industries)
- HCPs who have participated in the previous waves of the survey
- HCPs who have already 2 or more colleagues participating in the survey from the same practice in the same wave

Patient survey

The following exclusion criteria will be checked at the beginning of the web questionnaire:

- Patients (or caregivers) who may have conflicts of interest with the survey
- Patients (or caregivers) who have participated in the previous waves of the survey

9.2.3 Analysis population(s)

Analysable questionnaires are those submitted by the participant on the web, completed by phone or received by postal mail anonymously, and which do not have “I don’t know” as the answer to all questions. If the questionnaire is just filled on the web but not submitted, the questionnaire will be destroyed and will not be analysed.

9.2.4 Modalities of recruitment

9.2.4.1 HCP selection

HCPs will be identified from OneKey lists. A random stratified sampling method will be applied. As a first step, all lists will be merged, and then the eligible HCPs will be divided into homogeneous

groups, called strata, which are mutually exclusive (an HCP can only belong to one stratum). This stratification will be based on the following criteria:

Number of strata formed = number of countries * number of specialties

In order to fill-in each stratum of the sample survey from the IQVIA OneKey reference files, an independent sample will be selected per stratum through a simple random sampling without replacement.

In each specific stratum, HCPs will be contacted according to the order of draw in this stratum. If an HCP does not want to participate in the survey, the next one in order of draw will be contacted, and so on until the required number of HCPs is met. If the target for a stratum is not achieved after the end of the initial list, an additional randomly sampled list will be prepared, and the HCPs contacted until the goal is reached or no names are left in that stratum. If the complete list of the IQVIA OneKey reference files has been exhausted in any particular stratum, a strategy will be determined to adjust the sample size within stratum with associated weighting.

In web surveys, the number of HCPs to be contacted for reaching the required number of HCPs with analysable questionnaires is usually around ten times more than the expected final number.

9.2.4.2 Patient selection

Only HCPs (physicians) prescribing SULIQUA will be involved in patient recruitment. An invitation letter to participate in the study will be randomly given to patients treated with SULIQUA at physician offices. As in the case of HCPs, a patient can only participate in one wave of the survey. There will be no limit on the number of patients recruited per HCP. Patients' data will be anonymous when presented to the MAH.

The prescription of therapies is the sole responsibility of the patient's physician.

The patients who will be enrolled in the study, will be selected among the patients for whom the physician has decided to prescribe SULIQUA independently from study entry.

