9.6.2 Approaches for increasing response rates

People are increasingly contacted to participate in web or phone surveys. The overall response rate of participation remains low according to international studies (2) (3) (4). Holbrook et al. showed that the response rate to surveys continues to decline over time, but a lower rate does not appear to reduce the representativeness of a demographic survey (4). Van Geest et al. conducted a systematic review of 66 published reports on efforts to perform for improving response rates (5). Two general strategies were explored: incentives-based approaches and survey design-based approaches. Financial incentives, even little ones, were effective in improving physician response rates while non-monetary incentives were much less effective. These measures include the use of a short questionnaire, and questionnaires personalised, and approved by professional associations.

In order to increase the response rate among HCPs, three actions will be applied to this survey:

- A compensation fee will be proposed to HCPs for their participation in the survey
- All HCPs will be sent an e-mail or contacted by experienced operators of IQVIA Primary Intelligence with extensive experience in conducting health related surveys
- Each HCP will be emailed or called up to 3-5 times before being considered as “not reachable”, and reminders will be sent by email if IQVIA Primary Intelligence does not receive the web questionnaire

For increasing the response rate among the patients:

- The survey will be explained clearly through the HCPs, and the documentation will also clearly explain the importance of the patients' participation
- It will be ensured that patients participate anonymously in the survey
- Patients will be given the option to take the survey by paper or web questionnaire
- Recruiting HCPs will be provided with 10 patient kits (as there is no limit on number of patients recruited by a HCP, a refill will be done at HCP's request)
- No monetary or material incentives will be provided to patients, but a compensation fee will be proposed to HCPs for each patient participating in the survey
- The response rate will be monitored throughout the data collection period. If at the end of the inclusion period, the number of participants is insufficient, the inclusion period will be extended. Reminder notices and additional kits will be sent to HCPs who have been invited to participate, but not yet recruited any patients.

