9.6.6 Logistic aspects

For patient questionnaires, each recruiting HCP will hand over a patient kit. Refill of patient kits will be done at HCP's request. In the kit, the patient will find the survey questionnaire with a prepaid envelope for sending the survey back to IQVIA. It will also include a simplified guide for taking the survey online according to the patient's personal choice.

The patient questionnaire completion is estimated to take 15-20 minutes.

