9.7.2 Secondary analysis

Analysis of Participation rate

The following cases of total response and non-response will be identified and described for HCPs:

- Targeted HCPs: HCPs reached to whom an e-mail or e-mail has been sent or have been called
- Contacted HCPs: HCPs who have received the e-mail or have answered the phone call.
- HCPs who agreed to participate: HCPs willing to participate in the survey (e.g. by phone or by clicking on the link provided in the recruitment e-mail) or in the patient's recruitment
- HCPs with submitted questionnaire: HCPs who actually answered the questionnaire through the end and submitted it. (One or some missing answers are allowed across the questionnaire.)
- HCPs who recruited patients: HCPs with at least 1 patient having actually answered the questionnaire and submitted it by paper or web

For patients/caregivers, more simplified definitions will be calculated based on the following definitions:

- Contacted patients/caregivers: those who have been asked by HCPs to participate
- Patients/caregivers who agreed to participate: those who accepted the questionnaire
- Patients/caregivers with submitted questionnaire: those who actually answered the questionnaire and submitted it by paper or web

The participation rates of HCPs will be examined via the following ratios:

- Contact rate = Number of contacted HCPs divided by the total number of targeted HCPs
- Response rate = Number of HCPs who agreed to participate (in the survey or in recruitment of patients) divided by the total number of invited HCPs
- Cooperation rate = Number of HCPs with submitted questionnaire divided by the total number of HCPs who agreed to participate
- Refusal rate = (Number of contacted HCPs minus the number of HCPs who agreed to participate) divided by the total number of contacted HCPs

The participation rates will be presented by country and specialty.

The screening log which includes the HCPs' characteristics will enable to compare the participating and non-participating HCPs' profile to check if there is a selection bias.

Effect of EMs variations among targeted countries on success factors:

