1	None (0)	()
2	1-5	()
3	6-10	()

4	11-20	()
5	>20	()

Data: Single punch

Q9 and Q10 for dispensers [D2a=3]

Q9 How many prescriptions for Suliqua have you been queried about or returned for clarification by the prescriber in the last 3 months?

1	None (0)	()
2	1-5	()
3	6-10	()
4	11-20	()
5	>20	()

Data: Single punch

Q10 How many prescriptions for Suliqua have you been queried about for clarification by patients in the last 3 months?

1	None (0)	()
2	1-5	()
3	6-10	()
4	11-20	()
5	>20	()

Data: Single punch

Another survey will be conducted to assess the knowledge and understanding of the key safety messages in the Patient Guide among patients treated with Suliqua. Would you like to help us, by giving the survey questionnaire to your patients? They will then complete an online/paper questionnaire anonymously without your involvement. You will be paid: **XX € / completed patient/caregiver questionnaire. IQVIA will re-contact you in order to make the necessary arrangements for patient survey distribution.**

1. Yes, I would like to distribute the patient survey among my patients. I agree to be contacted again for this purpose.
2. No

Data: Single punch

If yes, display :

1. I would like to be contacted by IQVIA using the default contact information
2. I would like to provide different contact information

Data: Single punch

If item 2 selected then show:

Please confirm your details:

YOUR NAME:	
E-MAIL ADDRESS:	
ADDRESS:	

Note:

Blue is for data and will not appear in questionnaire,

Green is for internal use and will not appear in questionnaire,

Black will be in the questionnaire.

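### The protocol says patients are invited randomly, but it gives no random mechanism, so the patient sample is in effect a convenience sample handed out by prescribing physicians

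*Protocol*

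**What the plan says.** On patient selection, section 9.2.4.2 states: "An invitation letter to participate in the study will be randomly given to patients treated with SULIQUA at physician offices". It adds "Only HCPs (physicians) prescribing SULIQUA will be involved in patient recruitment" and "There will be no limit on the number of patients recruited per HCP". The Abstract repeats the claim of random invitation and names the HCP as the person who gives the letter.

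The field procedure is in two other places. Section 9.6.2 says "Recruiting HCPs will be provided with 10 patient kits", refilled on request, and section 9.6.6 says "each recruiting HCP will hand over a patient kit". Section 9.6.2 also says "a compensation fee will be proposed to HCPs for each patient participating in the survey"; the closing item of Annex 2 words the payment unit as a "completed patient/caregiver questionnaire".

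Section 9.7.2 defines three patient counts. The first is "Contacted patients/caregivers: those who have been asked by HCPs to participate"; the others are those who accepted the questionnaire and those who submitted it. Section 9.3.1 lists HCP and patient participation information as coming from the HCP questionnaire.

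Section 9.9 acknowledges possible selection bias in patient participation and cluster sampling bias. It says that surveyed patients cannot be compared with the general SULIQUA patient population.

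**The concern.** The word *randomly* tells a regulator that chance decided who was invited. Nothing in the protocol makes that so. The physician who distributes kits is often also the person who trained the patient or supplied the patient guide, and the patient success factors measure receipt of the guide, understanding and use. If invitation depends on how well informed a patient is, the estimated proportions shift. The verdict rests on point estimates: at least two of three proportions at or above 80%.

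The protocol itself says that representativeness cannot be checked afterwards. Invitation is therefore the step at which such bias has to be limited, or at least recorded. This is field procedure, not something usually left to a statistical analysis plan.

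**Working it through.** **1. What *randomly* amounts to.** Compare the two samples in the same protocol.

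| | HCPs (9.2.4.1) | Patients (9.2.4.2, 9.6.2, 9.6.6) |
|---|---|---|
| Frame | OneKey lists | none |
| Draw | simple random sampling without replacement in each stratum | none described |
| Order of contact | order of draw | none described |
| Record of those not taking part | screening log | none described |
| Who issues the invitation | the survey team | the prescribing physician |

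A physician with 10 kits and this text has no rule for deciding who receives one. The choice falls to the physician by default.

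**2. The plan's own figure.** Section 9.5.1 uses n = P(1−P)z²/e². With P = 0.50, z = 1.96 and e = 0.08, n = 150.06, so the stated 150 per wave is reproduced. The formula presumes a simple random sample of independent respondents. The arithmetic is right; the sampling assumption is what the field procedure does not deliver.

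**3. Illustration of selection.** Let p be the true proportion passing a success factor. Let r be the assumed ratio of the chance of being invited and returning the form, for patients who would pass against those who would not. The expected observed proportion is pr/(pr + 1 − p). Neither p = 0.70 nor any r comes from the documents.

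- r = 1.5: 1.05/(1.05 + 0.30) = 0.778
- r = 2: 1.40/(1.40 + 0.30) = 0.824
- r = 3: 2.10/(2.10 + 0.30) = 0.875
- r = 1/1.5 (less informed patients preferred): 0.70/(0.70 + 0.30 × 1.5) = 0.609
- Ratio needed for 80%: r = (0.80 × 0.30)/(0.70 × 0.20) = 1.71

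With 150 independent patients, the binomial chance that this one proportion reaches 120/150 is 0.4% without selection, and 29%, 81% and 99.7% at r = 1.5, 2 and 3.

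**4. One factor is not enough.** The verdict needs two of three proportions at 80%, so the preference must act on at least two. Factors 1 and 3 are linked. A patient who answers No to Q5 skips one item of Q6 and one of Q7, which leaves 6 of the 8 factor-3 items. Read as a count, the rule of at least 6 then requires all six. Read as 75% of the items asked (4.5), it requires five.

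**5. Source of the patient counts.** Submitted forms can be counted. Annex 2 has no item on patients asked or accepting, and the request to help with recruitment comes at its end, before any kit is handed out. The screening log in section 9.7.2 holds HCP characteristics. Kits shipped give only an upper bound on patients asked.

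**The case against.** The strongest reply is that no sentence says physicians choose. The text says the invitation is random, and an instruction sheet for physicians could supply the rule. That is fair as to wording, and it is why the point concerns a missing mechanism, not a stated practice of picking patients. But no such sheet is described, and the described steps contain no random element.

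Second, section 9.9 is not silent: it discloses possible patient selection bias and cluster sampling bias. This stands. What it lacks is physician discretion as a source, and any patient-level mitigation.

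Third, a reader might infer that the fee and the absence of a cap push physicians towards informed patients. The documents do not support that. The fee is paid per participating patient or completed form whatever the answers, so it rewards volume, and patients answer anonymously without the physician's involvement. Having no cap lets a physician invite every patient, which leaves less room for picking; it is a clustering matter. Neither should be cited as evidence of preference.

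Fourth, the guide may come from a pharmacist, so receipt is not purely the recruiting physician's work. Easy-to-reach or recently started patients could equally be favoured. Both points stand and leave the direction of bias open.

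**Conclusion.** The concern holds in this form: the protocol labels as random an invitation step for which it provides no random mechanism, and the result is in effect a physician-selected convenience sample. The patient counts for asked and accepted have no data source.

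A reader might go further and conclude that the results are biased towards finding the measures effective. That is not shown. The size and direction are unknown, and the 78% and 82% figures rest on an assumed true 70% and assumed preferences of 1.5:1 and 2:1. At 1.5:1 the expected proportion stays below 80%; crossing needs about 1.7:1, acting on at least two of the three factors. What the illustration does show is that a moderate preference could matter against a fixed 80% line, and that the plan as written could neither prevent nor detect it.

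**What to change.** For Wave 3, and for any Wave 2 fieldwork still open:

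- In section 9.2.4.2 and the Abstract, replace the claim of random invitation with consecutive distribution: from receipt of the kits, one numbered kit to each successive eligible SULIQUA patient.
- Have the physician mark each kit number as offered and accepted, or offered and declined, and return the tally. This supplies the section 9.7.2 counts. Correct section 9.3.1, which points to the HCP questionnaire for them.
- Describe forms already collected as physician-distributed, not random.
- Add physician discretion over invitation to section 9.9.
- Show patient results by wave.

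The cost is an instruction sheet, a tally form and a small recording burden; section 10.3.3 already compensates an estimated 5 minutes per patient recruited. Consecutive distribution over-represents frequent attenders and still depends on physicians following the rule and reporting refusals. Wave 1 collection began in September 2019 and Wave 2 was scheduled from January 2020, both before the amendment of February 2020. The new rule would therefore differ from that used earlier, which is why results should be shown by wave.
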